# 8.9.1.3 Selection Bias

Differential loss to follow-up is a type of selection bias that poses a potential threat to the internal validity of any study, including randomized studies. Loss to follow-up can be broadly conceptualized as any termination of treatment prior to the administrative end of the study, including, but not limited to, discontinuation of assigned treatment, switching to the alternate study arm, drop-out as a result of change in health plan, drop-out due to illness/frailty, etc. If all disenrollment occurred at random (eg, because of the loss of a health plan at the end of the calendar year), there would be loss in precision, but no increase in bias of the effect estimate. In most studies using claims data, however, we assume that health plan disenrollment, particularly mid-year disenrollment, does not occur at random. Under these circumstances, we must use methods such as IP weights to account for differential health plan disenrollment. These methods have been

described earlier and assume that we are able to identify strong confounders of disenrollment / switching / discontinuation and the outcome. Such covariates can be difficult to identify in claims data, but recent research has elucidated several baseline predictors of health plan disenrollment (Butler et al, 2019). More relevant predictors may be time-varying covariates (such as medical history indicators) that occur proximate to health plan disenrollment. We will explore inclusion of time-varying covariates in our censoring models, to address differential health plan disenrollment / switching to an alternate CGRP mAb / discontinuation of study medication.

# 8.9.1.4 Confounding

A few studies suggest that there is a positive correlation between cigarette smoking and migraine (Sacco and Kurth, 2015; Le et al, 2011; Winsvold et al, 2011), and other studies describe a three- to nine-fold increased risk of ischemic stroke in migraineur women who smoke (Chang et al, 2019; Tzouiro et al, 1993). Smoking is a confounder in our study but is unmeasured in claims data. Estimates of the relative risk for our two cardiovascular outcomes (acute MI and stroke) may be biased upward or downward in a comparative study when an important confounder is not accounted for in the analysis. We propose the use of simple quantitative bias methods to provide a corrected effect estimate for the case of a dichotomous exposure, a dichotomous outcome, and an unmeasured but known dichotomous confounder (Lash et al, 2009).

When exposure, confounder, and outcome are dichotomous, accounting for confounder bias is possible if three parameters are known:

- The hypothesized association between the known but unmeasured confounder (C) and the outcome (or disease, D), ie, the risk ratio (RRCD). The relevant effect estimate chosen to describe the association between the unmeasured confounder and the outcome should be the same as the effect estimate used to describe the association between the exposure and the outcome in the comparative analysis. For our study the effect estimate of interest is the risk ratio.
- 2. The hypothesized proportion of subjects with the confounder in the exposed group,  $p_1$
- 3. The hypothesized proportion of subjects with the confounder in the unexposed group,  $p_0$

These bias parameters can be estimated from literature values, or they can be based on the experience of the investigator. A range of values can also be substituted to form a sensitivity analysis, to investigate the degree to which the bias must be present before the study conclusions are affected. We will use bias parameters identified from the

literature as our starting point, and then undertake additional sensitivity analyses by specifying a range of values for the bias parameters around the initial starting values. The goal of the quantitative bias tool in this case is to provide an adjusted effect estimate, accounting for the bias introduced by the unmeasured confounder.

The estimate of the observed effect estimate in the weighted cohort, not accounting for bias as a result of a missing confounder, will be calculated in the usual way:

$$\widehat{RR} = \frac{a \ (b+d)}{b \ (a+c)}$$

where a, b, c, and d are the counts in the 2x2 table for the four combinations of outcome and exposure, and m and n are the column totals:

	Exposure +	Exposure -
Outcome +	а	b
Outcome -	С	d
Total	m	n

If any of the counts are zero, then a continuity correction of +1/2 will be added to all the cells in the table, before any further calculations. The 95% confidence interval (CI) for the RR is calculated using the large sample formula:

$$\exp\{\ln(\widehat{RR}_{Obs})\pm 1.96 \times xSE(\ln \widehat{RR}_{Obs})\}$$

where,

SE
$$(\ln R R_{obs}) = \sqrt{\frac{1}{a} - \frac{1}{m} + \frac{1}{c} - \frac{1}{n}}$$

The adjusted RR, accounting for the unmeasured confounder, are estimated as follows:

$$\widehat{RR}_{Adjusted} = \widehat{RR}_{Obs} \ge x \frac{RR_{CD}p_0 + (1-p_0)}{RR_{CD}p_1 + (1-p_1)},$$

In addition to undertaking bias analyses for a missing confounder, we will also estimate the relative risk of the cardiovascular outcomes in a subset of 'apparent smokers,' who will be identified by prescription medications approved for smoking cessation.

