#### 8.5 Study Size

Based on recent analyses (Amgen Study 20200218) to evaluate the rate of hypertension in migraine patients, the following number of patients with a migraine preventive treatment were identified within the Marketscan® Early View claims database from May 2018 through January 2020:

- 15212 erenumab-aooe users
- 17239 galcanezumab-gnlm or fremanezumab-vfrm users
- 9242 onabotulinumtoxinA users

These migraine preventive treatment users were required to be 18-64 years of age, have a diagnosis for migraine based on ICD-10-CM diagnosis codes or one prescription order for a triptan/ergot in the prior 12 months, continuous enrollment in the claims database for at least 12 months prior to the index date, and no prior prescription for any medication targeting the CGRP pathway. These counts were generated before the February 2020 approval of eptinezumab-jjmr. Assuming a conservative 3-month growth rate of 15%, the expected number of new users during the study period (17 May 2018 – 31 May 2020) will be ~20 000 new users of erenumab-aooe, ~23 000 new users of other mAbs targeting the CGRP pathway, and ~13 000 new users of onabotulinumtoxinA. While new users of the SOC migraine preventive medications (anti-epileptics) were not evaluated, other analyses in the Optum electronic health record database suggest that this new user cohort will be at least as large as the erenumab-aooe new user cohort.

Table 2 provides the 95% confidence interval estimates for various potential risk estimates of the three cardiovascular outcomes (0.2%, 0.5%, 1%, 3%, 5%, 20%, and

30%) based on the projected sample size described above for erenumab-aooe, other mAbs targeting the CGRP pathway, and onabotulinumtoxinA. The risk of acute MI and stroke is expected to be relatively rare across all new user cohorts, while the risk of hypertension is expected to be common.

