#### Table 2. 95% CI Estimates and Half-widths for a Range of Cardiovascular Outcome Values, Based on a Sample Size of 20 000 Erenumab-aooe Users, 23 000 Users of Other mAbs Targeting the CGRP Pathway and 13 000 Onabotulinumtoxin A Users

	Erenumab-aooe N = 20 000		Other mAbs Targeting the CGRP Pathway N = 23 000		OnabotulinumtoxinsA N = 13 000	
CV Outcome (%)	95% CI	Half-width of Cl	95% CI	Half-width of Cl	95% CI	Half-width of Cl
0.20	0.14, 0.26	0.06	0.14, 0.26	0.06	0.12, 0.28	0.08
0.50	0.40, 0.60	0.10	0.41, 0.59	0.09	0.38, 0.62	0.12
1.00	0.86, 1.14	0.14	0.87, 1.13	0.13	0.83, 1.17	0.17
3.00	2.76, 3.24	0.24	2.78, 3.22	0.22	2.71, 3.29	0.29
5.00	4.70, 5.30	0.30	4.72, 5.28	0.28	4.63, 5.37	0.37
20.0	19.5, 20.6	0.55	19.5, 20.5	0.52	19.3, 20.7	0.69
30.0	29.4, 30.6	0.64	29.4, 30.6	0.59	29.2, 30.8	0.79

Abbreviations: CI: confidence interval; mAbs: monoclonal antibodies; CGRP: calcitonin gene-related peptide

Table 3 provides a range of detectable risk ratios for two outcomes of interest (acute MI and stroke), assuming 80% power, alpha-level of 0.05, and equal number of patients in each medication cohort, if a comparative analysis of the erenumab-aooe cohort to each comparator cohort (other mAbs targeting the CGRP pathway, selected SOC migraine preventive medications (anti-epileptics), or selected onabotulinumtoxinA ) were conducted. This table assumes a background rate of acute MI of 0.15 per 100 PYs and a background rate of stroke of 0.60 per 100 PYs (Gill et al, 2020).

 Table 3. Detectable Risk Ratios for Two Cardiovascular Outcomes

	Total Population in Each Medication Cohort						
Outcome	N = 13 000	N = 17 000	N = 20 000	N = 25 000			
Acute MI	2.10	1.94	1.85	1.75			
Stroke	1.58	1.51	1.46	1.41			

The estimates provided above are for informational purposes only. The final sample size for the study will change due to the criteria applied during the conduct of the protocol.

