### Decision to Proceed to Comparative Analyses

The decision to move forward with the comparative analysis for either the acute MI or the stroke outcome will be made after assessment of covariate balance across treatment groups (eg, based on an absolute standardized mean difference of > 0.10 for covariates included in the PS model, and adequate overlap in the PS across treatment arms), null findings for the final set of negative control outcomes (ie, posterior probability > 90% that the level of bias is less than 10% of the null), and sufficient sample size to detect a risk ratio of 2.0 or greater. For the relatively rate outcome of acute MI, a total of 15,000 patients in each comparator arm will be needed in order to detect a risk ratio of 2.0 or greater, assuming 80% power and a background rate of acute MI of 0.15 per 100 person-years. In contrast, for the outcome of stroke, 3,750 patients will be required in each treatment arm to detect a risk of 2.0 or greater, assuming 80% power and a background rate of stroke of 0.60 per 100 peson-years.

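### Section 8.9.1.4: the standard error of ln(RR_Obs) uses 1/c where the plan's own table requires 1/b, so the bias-analysis interval is too narrow

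*Protocol*

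**What the plan says.** Protocol section 8.9.1.4 treats smoking as a confounder that claims data do not measure, and plans a simple quantitative bias analysis for the acute MI and stroke comparisons. The starting point is described as "The estimate of the observed effect estimate in the weighted cohort, not accounting for bias as a result of a missing confounder". It is computed as RR = a(b+d)/[b(a+c)], "where a, b, c, and d are the counts in the 2x2 table for the four combinations of outcome and exposure, and m and n" being the column totals. The table has exposure in columns and outcome in rows:

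- a = exposed with the outcome, b = unexposed with the outcome
- c = exposed without the outcome, d = unexposed without the outcome
- m = a + c, n = b + d

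The section continues: "The 95% confidence interval (CI) for the RR is calculated using the large sample formula". The interval is exp{ln(RR_Obs) ± 1.96 × SE}, with SE printed as sqrt(1/a − 1/m + 1/c − 1/n). RR_Adjusted is then RR_Obs multiplied by a factor built from RR_CD, p0 and p1. No separate interval is given for RR_Adjusted, and no other section restates or corrects the SE.

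**The concern.** The second half of the printed SE, 1/c − 1/n, pairs a cell from the exposed column with the total of the unexposed column. The large-sample variance of a log risk ratio has one term per arm, each of the form 1/(events) − 1/(patients). For the comparator arm, in this layout, that is 1/b − 1/n. The printed form would be right for a table with exposure in rows, so it looks carried over from another layout.

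Both outcomes are rare, so c is close to 20,000 and 1/c is close to zero. The comparator arm's event variability therefore almost vanishes from the interval. The bias analysis is meant to show how strong an unmeasured confounder would have to be before the conclusions change. An observed RR with an interval that is too tight makes that starting point look more precise than it is.

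**Working it through.** **Inputs.**
- Table layout, RR and printed SE: section 8.9.1.4.
- Rates: "a background rate of acute MI of 0.15 per 100 PYs and a background rate of stroke of 0.60 per 100 PYs" (section 8.5, with Table 3). Assumption: the 1-year risk equals the rate, so 0.0015 and 0.006.
- Cohort sizes: about "20 000 new users of erenumab-aooe, ~23 000 new users of other mAbs targeting the CGRP pathway, and ~13 000 new users of onabotulinumtoxinA" (section 8.5). I also use 20,000 vs 20,000, since Table 3 assumes equal cohorts and the anti-epileptic cohort is expected to be at least as large as the erenumab cohort.
- Effect sizes: RR 1 for the null, and RR 2 because section 8.7.2.4 requires "sufficient sample size to detect a risk ratio of 2.0 or greater".

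The protocol gives no numerical SE or interval for this formula, so there is no stated figure to reproduce.

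**Step 1: variance from the plan's own RR.** RR = (a/m)/(b/n). By the delta method, Var[ln(a/m)] = 1/a − 1/m and Var[ln(b/n)] = 1/b − 1/n. With independent arms, SE = sqrt(1/a − 1/m + 1/b − 1/n).

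**Step 2: two checks that the printed form is not a matter of notation.**
- *Sign.* With 240 strokes in 20,000 exposed and a comparator of 13,000, c = 19,760 and 1/c − 1/n = 0.0000506 − 0.0000769 = −0.0000263. An arm cannot contribute negative variance.
- *Relabelling.* Swapping the arms must leave the SE of ln(RR) unchanged. At 20,000 per arm the printed form gives 0.129 for 60 vs 30 events and 0.182 for 30 vs 60. The correct form gives 0.223 both ways.

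**Step 3: size.** One case in full, stroke at RR 2, 240/20,000 vs 78/13,000:
- Printed: sqrt(0.0041667 − 0.0000500 + 0.0000506 − 0.0000769) = sqrt(0.0040904) = 0.064
- Correct: sqrt(0.0041667 − 0.0000500 + 0.0128205 − 0.0000769) = sqrt(0.0168603) = 0.130
- Ratio 0.49; coverage = 2Φ(1.96 × 0.493) − 1 = 0.67

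Other cases, 20,000 exposed throughout:

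| Comparator n | Outcome, RR | a, b | SE printed | SE correct | Ratio | CI printed | CI correct | Coverage |
|---|---|---|---|---|---|---|---|---|
| 20,000 | MI, 1 | 30, 30 | 0.182 | 0.258 | 0.71 | 0.70–1.43 | 0.60–1.66 | 83% |
| 20,000 | MI, 2 | 60, 30 | 0.129 | 0.223 | 0.58 | 1.55–2.57 | 1.29–3.10 | 74% |
| 20,000 | Stroke, 1 | 120, 120 | 0.091 | 0.129 | 0.71 | 0.84–1.20 | 0.78–1.29 | 83% |
| 20,000 | Stroke, 2 | 240, 120 | 0.064 | 0.111 | 0.58 | 1.76–2.27 | 1.61–2.49 | 74% |
| 23,000 | Stroke, 1 | 120, 138 | 0.091 | 0.124 | 0.73 | 0.84–1.20 | 0.78–1.28 | 85% |
| 23,000 | Stroke, 2 | 240, 138 | 0.064 | 0.106 | 0.60 | 1.76–2.27 | 1.62–2.46 | 76% |
| 13,000 | Stroke, 1 | 120, 78 | 0.091 | 0.145 | 0.63 | 0.84–1.19 | 0.75–1.33 | 78% |
| 13,000 | Stroke, 2 | 240, 78 | 0.064 | 0.130 | 0.49 | 1.76–2.27 | 1.55–2.58 | 67% |

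For rare outcomes the ratio is close to sqrt(b/(a+b)). It depends on how the events divide between the arms and hardly at all on the absolute rate.

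**Step 4: simulation.** With 400,000 binomial replicates at 20,000 per arm, the printed formula covers 83.5% (MI) and 83.4% (stroke) at RR 1, and 74.1% and 74.3% at RR 2. The corrected formula covers 95.1% to 95.3%.

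**The case against.** *It may be a misread letter.* The neighbouring formula lines contain stray symbols from the PDF reading, so a b read as c cannot be ruled out. However, b and c are read correctly in the RR formula just above, and the printed expression is exactly the one for a table with exposure in rows. A slip in the source is more likely; a look at the PDF settles it.

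*The reach is limited.* This stands. The interval is defined for RR_Obs only, in a bias analysis that follows comparisons which are themselves conditional. A reader might infer that the main RR(t) intervals are wrong too. The protocol promises 95% intervals for RR(t) in section 8.7.2.4 but does not say that they use this formula. A reader might also infer that the study would declare significance, or robustness to smoking, on the faulty interval. No such rule is attached to it, and the stated aim is an adjusted effect estimate over a range of bias parameters.

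*Weighting.* One could read the cell counts as raw and conclude that the formula ignores the weights. The protocol does not say raw; it introduces the estimate as one in the weighted cohort. How variance is handled under weighting is a separate matter and no part of this point.

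*Low coverage against 13,000.* An MI example there would not be apt: section 8.7.2.4 asks for 15,000 per arm for MI, and onabotulinumtoxinA is projected at about 13,000. Stroke needs 3,750 per arm, so the stroke example meets that size condition and gives the same 67%.

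**Conclusion.** The printed SE contradicts the table and RR formula in the same section and is wrong as written. The interval for RR_Obs is 27% (ratio 0.73) to 51% (ratio 0.49) too narrow on the log scale. At RR 1 the two-sided error is about 15% to 22% instead of 5%.

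These figures assume that the 1-year risk equals the stated rate, that the projected cohort sizes hold, and simple binomial sampling. The first assumption matters little while the outcomes stay rare. The second matters more: the understatement shrinks as the comparator grows, and for the anti-epileptic cohort the protocol gives only a lower bound, so the results at 20,000 are the unfavourable end for that comparison.

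The error reaches the RR_Obs interval and, for fixed bias parameters, any RR_Adjusted interval that carries over the same SE. The RR_Obs and RR_Adjusted point estimates are unaffected. The documents do not support extending it to the main RR(t) intervals or to any decision rule.

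**What to change.** In section 8.9.1.4, replace 1/c by 1/b, so that SE(ln RR_Obs) = sqrt(1/a − 1/m + 1/b − 1/n), after checking the letter against the PDF. If the formula has already been programmed, make the same change there. The cost is one symbol; the only consequence is wider, correct intervals.

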# 8.9.2 External Validity of Study Design

The primary analyses for this study are limited to individuals with employer-sponsored health coverage included in the MarketScan® Commercial and Medicare Supplemental

medical claims database. Thus, results of this analysis may not be generalizable to individuals with other types of insurance coverage or those without health insurance. Also, for individuals with employer-sponsored health insurance, the results of these analyses are likely also not generalizable to those who first obtained their medication through the free drug programs.

### 8.9.3 Analysis Limitations

This study is based on an analysis of automated medical and prescription claims. While claims data are extremely valuable for the efficient and effective examination of health care outcomes, treatment patterns, and health care resource utilization, all claims databases have certain inherent limitations because the claims are collected for the purpose of payment and not research. Presence of a claim for a filled prescription does not indicate that the medication was consumed or that it was taken as prescribed. Medications obtained over-the-counter or provided as samples by the physician will not be observed in claims data. Presence of a diagnosis code on a medical claim is not positive presence of disease, as the diagnosis code may be incorrectly coded or included as rule-out criteria rather than actual disease. Duration of follow-up can be limited in claims data due to individuals changing health insurance plans.

There are challenges to evaluating drug-induced hypertension when using administrative claims data. For example, it can be difficult in claims data to distinguish between transient and true hypertension given issues of 'rule-out' diagnoses, 'white coat' hypertension, and hypertension caused by other medical conditions (eg, migraine pain) and not the medication. Also, the blood pressure measurements on which the hypertension diagnosis is based can be inaccurate regardless of the healthcare setting.

Changes in blood pressure are difficult to assess, even in the context of randomized studies with active data collection. In real world settings, changes in blood pressure may be asymptomatic and under-ascertained versus the more acute outcomes of stroke and acute MI which require more immediate medical attention. Finally, hypertension has been conceptualized more as a risk factor and not strictly a cardiovascular outcome in validation studies using claims data. Modification of these validated algorithms is necessary when hypertension is evaluated not as a baseline characteristic but as a drug-induced outcome.

### 8.9.4 Limitations Due to Missing Data and/or Incomplete Data

As described in Section 8.9.1.1, because of available free drug coupon programs for mAbs targeting the CGRP pathway, prescriptions for initial use of the medications will be

missing for some patients. Consequently, when using claims data, the CGRP mAb medication cohorts will include incident users of CGRP mAbs, as well as prevalent users of CGRP mAbs.

### 8.10 Other Aspects

Not applicable.

# 9. Protection of Human Subjects

### 9.1 Institutional Review Board

This is a retrospective cohort study using the MarketScan® Commercial and Medicare Supplemental medical claims database and is considered secondary data collection. No primary data collection will occur, consent is not needed, and Institutional Review Board approval is not required. The data does not include any individually identifiable data. All database records are de-identified and fully compliant with the United States patient confidentiality requirements, including the Health Insurance Portability and Accountability Act of 1996.

# 10. Collection, Recording, and Reporting of Safety Information and Product Complaints

### 10.1 Safety Collection, Recording and Submission to Amgen Requirements

This study is analyzing secondary data from the MarketScan® Commercial and Medicare Supplemental medical claims database. The safety outcomes that are listed in Section 8.3.2 will be documented and analyzed in this study. These will be reported in aggregate in the final study report as incidence rates or cumulative incidence (ie risk). See Section 8.3.2 for safety outcomes and definitions. Submission of safety outcomes as individual safety reports to Amgen is not required. Reportable events suspected to be related to any medicinal product should be reported to the local authority in line with the local country requirements.

# 11. Administrative and Legal Obligations

# 11.1 Protocol Amendments and Study Termination

Amgen may amend or terminate the protocol at any time.

# 12. Plans for Disseminating and Communicating Study Results

# 12.1 Publication Policy

The results of the study will be submitted for publication.

Authorship of any publications resulting from this study will be determined on the basis of the International Committee of Medical Journal Editors (ICJME) Recommendations for the Conduct, Reporting, Editing, and Publication of Scholarly Work in Medical Journals, which states:

- Authorship credit should be based on (1) substantial contributions to conception and design, acquisition of data, or analysis and interpretation of data; (2) drafting the article or revising it critically for important intellectual content; (3) final approval of the version to be published and (4) agreement to be accountable for all aspects of the work in ensuring that questions related to the accuracy or integrity of any part of the work are appropriately investigated and resolved. Authors should meet conditions 1, 2, and 3 and 4.
- When a large, multicenter group has conducted the work, the group should identify the individuals who accept direct responsibility for the manuscript. These individuals should fully meet the criteria for authorship defined above.
- Acquisition of funding, collection of data, or general supervision of the research group alone does not justify authorship.
- All persons designated as authors should qualify for authorship, and all those who qualify should be listed.
- Each author should have participated sufficiently in the work to take public responsibility for appropriate portions of the content.

All publications (eg, manuscripts, abstracts, oral/slide presentations, book chapters) based on this study must be submitted to Amgen for corporate review. The vendor agreement will detail the procedures for, and timing of, Amgen's review of publications.

